2.2 DETAILED DESCRIPTION OF STUDY DESIGN

Study Visits and Procedures:

Timepoint	Task
Pre-Enrollment	Screening for inclusion and exclusion criteria
Before Administration of Study Drug, 0h	PCAS MD Baseline, Baseline lab data, ECHO and LSCI
During Study Drug Administration, 0h-13h	Vitals, Labs, ECHO, LSCI
Retrospective Baseline Data	Demographics, OHCA data, Clinical Lab data
Day 1 Post ROSC	VS, Labs, Clinical Lab data, PCAS MD Daily data, Interventions, Medications, SOFA
Day 2 Post ROSC	VS, Labs, Clinical Lab data, PCAS MD Daily data, Interventions, Medications, SOFA
Day 3 Post ROSC	VS, Labs, Clinical Lab data, PCAS MD Daily data, Interventions, Medications, SOFA
Discharge	Survival, CPC, mRS, CPC-E, Barthel ADL, NYHA Class, Location
30d Follow Up	Survival, CPC, mRS, CPC-E, Barthel ADL, NYHA Class, Location
90d Follow Up	Survival, CPC, mRS, CPC-E, Barthel ADL, NYHA Class, Location

****Please note that the 0h ECHO and LSCI may be collected up to one hour after the administration of the study drug to avoid issues with timing of enrollment.**

The majority of data, including all clinical lab data, that is collected for this study will be gathered during a single hospitalization. All labs will be collected within 30 minutes of their assigned time.

Follow-up data that will be obtained will not require a subsequent visit, but rather just a phone call.

Most of the baseline data elements can be effectively gathered retrospectively and will not be needed prior to starting the study drug. A small number of data elements will indeed need to be captured before study drug is administered but these can be done fairly rapidly to preclude delays in therapy onset. The same is true for data elements in days 1-3 post-arrest (0-24 h after ROSC is considered day 1)

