The following data elements will be collected during the course of the study at the times indicated. Data elements marked with an asterisk indicate variables or outcomes essential for conduct of the study and analysis of efficacy and/or safety. These data elements should be obtained in all subjects with no missing data expected. In addition to these data elements, we are collecting a large amount of secondary data intended for use in mechanistic studies and hypothesis generation. In many cases, these data elements WILL NOT be able to be collected in all subjects. Such missing data will be handled as designated within an a priori statistical analysis plan but the presence of missing data will in no way impede our ability to meet the objectives of this phase 2 RCT.

BASELINE DATA

- *Date of OHCA
- *Time of OHCA (If not available we will use Time of ROSC after subtracting estimated no flow and CPR time based on transfer records/physician report)
- Witnessed
- Bystander CPR
- EMS Call Date
- EMS Call Time
- EMS Arrival Date
- EMS Arrival Time
- No flow time
- CPR (low flow) time
- Presenting rhythm
- *Date and Time of ROSC (If not available we will use ED admission date/time from referring hospital record. If unavailable, stat medevac call date/time minus 30 mins. If unavailable, time of arrival minus 15 min)
- PCAS ID
- *Last name
- *First name
- *Date of Birth
- *Medical record number
- Marital status
- Race/Ethnicity
- *Male Sex
- *Height
- *Weight
- Post-resuscitation chest pain

- Charlson Comorbidity
- Age Adjusted for Charlson Comorbidity Index (CCI)
- *New York Heart Association (NYHA) class pre-OHCA (if no surrogate is present and no medical records are found on the subject this will be assumed to be NYHA class I)
- Barthel ADL pre-OHCA
- Education level
- Private insurance
- Medicare
- Medicaid
- Employed
- Active smoker
- Smoker >20 pack-years
- Prior stroke
- Prior Coronary artery bypass grafting (CABG)
- Noninsulin-dependent diabetes mellitus (NIDDM2) type 2
- Insulin-dependent diabetes mellitus (IDDM2) type 2
- Diabetes mellitus (DM1) type 1
- Prior myocardial infarction (MI)
- Congestive Heart Failure (CHF)
- Chronic Obstructive Pulmonary Disease (COPD)
- Prior cardiac arrest
- Dementia
- Hyperlipidemia
- Hypertension
- Prior coronary stent
- Obstructive sleep apnea
- Pulmonary hypertension
- *Location pre-OHCA

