iNO is FDA approved for the treatment of pulmonary hypertension in the setting of hypoxic respiratory failure in neonates. It has been used off label extensively; primarily for the treatment of hypoxic respiratory failure and pulmonary hypertension. From these published studies, extensive safety data is available for a variety of endpoints with up to 2 year follow up.¹⁻⁶ In these studies efficacy as measured by increase in oxygenation was noted with doses as little as 1 ppm^{3,4} with rare cases of methemoglobinemia or excess NO₂ especially at the doses under 40 ppm. A recent meta-analysis of trials of iNO to treat ischemia reperfusion injury in humans demonstrated efficacy in the majority of studies and an excellent human safety profile, but noted no existing human evaluation of iNO in the setting of acute brain injury including OHCA.⁷

In human brain injury from stroke^{22,23} or trauma²⁴ the CSF levels of NO metabolites appear elevated by 24h with one study showing this effect is blocked using the inducible NO synthase inhibitor 1400W.²² Based on these reports it would appear a state of NO deficiency is highly likely at ROSC and persistent for up to 24h after ROSC. Thus the likely therapeutic window is from ROSC until 24h after ROSC.

Most studies that have demonstrated efficacy of iNO in animal models of CA or other IR injury have dosed the drug early (during CPR or at the time of ROSC). Only one study did a formal time course.³¹ In this report iNO started 2h after CA improved neurologic function/injury and survival but 6h later did not. Thus the therapeutic window is between CPR onset and <6h after ROSC. One study showed efficacy at 1h after ROSC.⁹ We selected a midpoint of 4h from ROSC as our latest time to initiate therapy but again stress that most data support earlier dosing either at the time of ROSC or during CPR. Thus our goal in designing a trial with recruitment under EFIC

is to enroll and dose patients as soon as possible after ROSC.

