Our patients will generally achieve ROSC in the field (pre-hospital). Most patients at PUH, our larger center, arrive as transports already 1-3h post-ROSC upon arrival. Thus at the time the subjects arrive in our center we will be under substantial time pressure to get them on study drug even to achieve the goal of dosing prior 4h of ROSC. Furthermore, **many of these patients are flown into our center or transported by ambulance with sirens activated, thus arriving without a family member from whom to obtain consent.**

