2.4 STUDY ENDPOINTS

Primary

Composite of in-hospital death, unfavorable discharge location, NYHA class III/IV heart failure at the time of discharge*

*In the setting of pre-existing heart failure or prior residence in an unfavorable location there must be at least a 1 class decrement (eg NYHA III -> IV)

Secondary

Functional

- Survival to hospital discharge, 30 and 90 days after initial OHCA
- Favorable cerebral performance category (CPC) defined as 1 or 2 at discharge, 30 and 90 days after initial OHCA
- Favorable modified Rankin score (mRS) defined as 0-3 at discharge, 30 and 90 days after initial OHCA
- Favorable discharge destination or location of residence (30 and 90 days after OHCA) defined as home or acute inpatient rehabilitation
- CPC-E at hospital discharge, 30 and 90 days after initial OHCA
- Barthel Index of Independence in Activities of Daily Living (ADL) at discharge, 30 and 90 days after OHCA

Neurologic

- Estimated likelihood of good neurologic outcome (0-100%) assessed by an experienced (>3y) member of the PCAS team blinded to treatment assignment on day 3-5 post-ROSC.
- Development of malignant EEG during hospitalization

- Time (in hours) to awakening from ROSC; defined as following commands (all values > 96h assigned 100)
- FOUR Motor + Brainstem scores on days 1-3 (requires 30 min off sedation; exclude endpoint if not medically permitted to pause sedation or paralysis)
- Presence or absence of upper and lower extremity somatosensory evoked potential N20 on comatose patients obtained any time after post-arrest day 1.
- Absolute value 24h after ROSC and change in value (24h vs 0h) of neuron specific enolase (NSE)
- EEG burst suppression ratio and change in suppression ratio
- EEG presence of dominant continuous background and reactivity to photic or tactile stimulation.

Cardiovascular

- Heart rate and mean arterial pressure (preferably off the arterial line) at 0-12 (hourly), 24h of study drug
- Persistent need for vasopressors in the first 24h after ROSC; defined as any use of norepinephrine, epinephrine, phenylephrine, dopamine or vasopressin for ≥ 3 h after study drug is initiated
- Persistent need of inotropes in the first 24h after ROSC; defined as any use of epinephrine, dobutamine, milrinone or isoproterenol for ≥ 3 h after study drug is initiated.
- ECHO measures (absolute values at end of therapy (12h) and change in 12h vs 0h):
 - tricuspid valve regurgitant velocity (TRV)

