3.3 EXCLUSION CRITERIA

Exclusion criteria do not change any subgroups.

- Traumatic etiology of OHCA
- Prisoner
- Known pregnancy
 - o B-HCG screening is NOT REQUIRED for enrollment in women of appropriate age
- Hemodynamic instability defined as:
 - o > 1 recurrent arrest prior to enrollment
 - o Inability to maintain mean arterial blood pressure (MAP) > 65 using vasopressors and inotropes (ie actively up titrating medications or giving fluid bolus)
- Cerebral edema defined as:

- Head CT grey-white ratio < 1.2
 - Fixed and dilated pupils without another explanation
- Malignant EEG upon presentation (not required as screening) defined as:
 - Myoclonic status epilepticus
 - Non-convulsive status epilepticus
 - Generalized periodic epileptiform discharges
- ROSC >3h from time of ED arrival (Treatment allocation must be within 4h so anything that will prevent this is reason for exclusion)
- Alert and interactive patient with minimal evidence of neurologic injury
- Plan to extubate within 12 hours
- PCAS opinion that patient will die with >95% likelihood. This may be based on:
 - Multiple medical comorbidities
 - Late discovery of DNR or advanced directive
 - Terminal diagnosis (other than OHCA; may have caused OHCA)
 - Clinical judgement based on current exam and data
- Known intracranial hemorrhage or acute cerebral infarction; Head CT is NOT REQUIRED prior to enrollment
- Patient is known to be taking PDE5 inhibitors, sGC stimulator, or has a known diagnosis of Chronic thromboembolic pulmonary hypertension (CTEPH), pulmonary hypertension (PAH), or erectile dysfunction
- Known enrollment in another acute interventional trial

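### The last fallback for a missing ROSC time is not limited to patients brought straight from the scene; for a transfer it would date ROSC about 0.75 to 2.75 hours too late

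*Combined protocol and SAP*

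**What the plan says.** The baseline data list in section 2.2 marks the date and time of ROSC as essential, with no missing values expected. It gives three substitutes in order:

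1. The referring hospital's ED admission: "If not available we will use ED admission date/time from referring hospital record".
2. 30 minutes before the medevac call.
3. "If unavailable, time of arrival minus 15 min".

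Each step depends only on the one before it being unavailable. The same list handles a missing arrest time by working backwards from ROSC: "If not available we will use Time of ROSC after subtracting estimated no flow and CPR time based on transfer records/physician report". It also collects EMS call and arrival times, no-flow time and CPR time, but it never works forwards from these to a missing ROSC time.

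On transfers, section 2.3.3 states: "Most patients at PUH, our larger center, arrive as transports already 1-3h post-ROSC upon arrival". On the treatment limit it states: "We selected a midpoint of 4h from ROSC as our latest time to initiate therapy". Section 2.4 counts one secondary endpoint from ROSC: "Time (in hours) to awakening from ROSC; defined as following commands".

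**The concern.** A gap of 15 minutes between ROSC and arrival may be about right for someone brought directly from the scene. It cannot describe a patient who went first to another hospital and arrives 1 to 3 hours after ROSC. The two transfer-specific substitutes come earlier in the list and should catch most transfers. However, section 2.3.3 says patients come by air or by ambulance, so a medevac call time need not exist for every transfer, and a referring record can be incomplete.

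At stake are the recorded interval from ROSC to study drug, which shows whether the 4-hour window was kept, and the recorded time to awakening. If the arrest time is also missing, it is computed from the substituted ROSC time and carries the same error. The plan has no field for the source of a ROSC time, so a reader of the data could not tell a documented time from a substituted one.

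**Working it through.** The plan gives no figure of its own on this point, so there is none to reproduce. The check is direct arithmetic.

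**Inputs**
- Substituted ROSC-to-arrival interval: 15 min = 0.25 h (section 2.2).
- True ROSC-to-arrival interval for a transfer, *t*: 1 to 3 h (section 2.3.3, most patients at the larger center).
- Latest start: 4 h after ROSC (section 2.3.3).
- Time from arrival to start of study drug, *d*: not given, so it is varied.
- Assumption: arrival means arrival at the study hospital. Section 2.3.3 uses the word that way; section 2.2 does not define it.

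**Formulas**
- True start = *t* + *d*.
- Recorded start = 0.25 + *d*.
- Error in the ROSC time = *t* − 0.25, always towards too late.
- Truly late but recorded as in time: *t* + *d* > 4 and 0.25 + *d* ≤ 4, so *d* lies above 4 − *t* and at or below 3.75.

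**Results by true interval at arrival**

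| *t* (h) | Error (h) | *d* giving a late start recorded as in time (h) | True start when recorded start is 4 h |
|---|---|---|---|
| 0.25 (direct arrival) | 0 | none | 4.00 h |
| 1 | 0.75 | 3.00 to 3.75 | 4.75 h |
| 2 | 1.75 | 2.00 to 3.75 | 5.75 h |
| 3 | 2.75 | 1.00 to 3.75 | 6.75 h |

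**Results by time from arrival to dosing**
- *d* = 1 h: recorded 1.25 h, true 2 to 4 h. The limit is kept.
- *d* = 2 h: recorded 2.25 h, true 3 to 5 h. The limit is broken when *t* exceeds 2 h, and the record does not show it.
- *d* = 3.75 h, the extreme: recorded 4 h, true 4.75 to 6.75 h.

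**Time to awakening.** Recorded value = true value − (*t* − 0.25), so 0.75 to 2.75 h too short. Section 2.4 assigns 100 to all values above 96 h, so nothing changes for a subject whose value exceeds 96 h on both clocks.

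**Troponin, as a check on reach.** Table 1 schedules draws at 0, 6 and 12 h from study drug start. At the extreme true start of 6.75 h, the last draw falls at 6.75 + 12 = 18.75 h after ROSC. That is inside the 24 h window on either clock, so no scheduled draw changes sides.

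**The case against.** The strongest reply is that the list already deals with transfers. Its first two steps apply only to them, so the natural reading is that the third serves direct arrivals. Section 5.1 adds that the physician reviews the arrest details before enrollment, so a transfer with no usable time at all should be rare. This stands as to size: the documents give no count and do not show that such a patient will occur. It does not answer the wording, which contains no restriction, and data staff will apply what is written.

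Several stronger conclusions are tempting, and the documents do not support them:

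- **That the rule admits late patients or disables the 3-hour exclusion.** A reader might infer this because the substituted interval is always 0.25 h. But the rule sits among the baseline data, of which section 2.2 says "Most of the baseline data elements can be effectively gathered retrospectively and will not be needed prior to starting the study drug". Eligibility is decided by a physician (sections 2.2 and 5.1), using a screening questionnaire that is not among the documents, and section 3.3 has its own catch-all: "Treatment allocation must be within 4h so anything that will prevent this is reason for exclusion". A value filled in afterwards can mislabel a late start but cannot cause one.
- **That power is lost.** Any dilution would come from late dosing itself, however ROSC was recorded. Assuming no benefit after 4 h is also unfounded, since section 2.3.3 puts the therapeutic window at under 6 h and describes 4 h as a chosen midpoint.
- **That the comparison is biased.** The rule is the same in both blinded arms, and the primary composite is assessed at discharge without reference to ROSC time.
- **That other ROSC-timed endpoints are materially damaged.** Scheduled troponin draws are unaffected, as shown. Persistent vasopressor and inotrope need is defined by at least 3 h of use after study drug starts; only the outer 24 h edge moves.

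The first substitute is imperfect too. It dates ROSC too late when ROSC occurred in the field and too early when the arrest occurred in the referring ED. The documents do not give the size of either error.

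**Conclusion.** The point holds as a minor recording error. For a transfer who reaches the last step, the written rule dates ROSC about 0.75 to 2.75 h too late. A start truly after 4 h can then be recorded as within 4 h, and time to awakening is recorded too short by the same amount.

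This rests on three conditions. The patient is a transfer with no ROSC, referring-ED or medevac time. Arrival means the study hospital. The 1 to 3 h range applies; it describes most patients at the larger center and is not a bound for every transfer. The arithmetic is certain under these conditions. The number of subjects is unknown and probably small, and no effect on eligibility, power or the primary comparison is shown.

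**What to change.** In the baseline data list of section 2.2, replace the order of substitutes for a missing ROSC time with:

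1. The documented arrest time plus no-flow and CPR time, or EMS times plus CPR time.
2. The referring hospital's ED admission time.
3. The medevac call time less 30 minutes.
4. Arrival less 15 minutes, only for patients brought directly from the scene.

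Only a documented arrest time should count in the first step, because an arrest time derived from ROSC would make the rule circular. For a transfer with no usable time, flag the ROSC time as estimated.

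Add one field for the source of each ROSC time, and repeat the summaries of ROSC-to-drug time and time to awakening in subjects with a documented ROSC time. Leave the eligibility wording in section 3.3 unchanged: writing a substituted time into an eligibility test would give direct arrivals the same fixed quarter hour.

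The cost is one reworded line, one data field and a repeat of two summaries. The inputs are already on the list, and section 3.2 already requires an estimate of the time from CPR start to ROSC, since ROSC must occur within 40 minutes. The downside is reliance on EMS and CPR fields that are not marked essential and may be missing in the same patients.

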Study Endpoints:	
Primary Composite of in-hospital death, unfavorable discharge location, NYHA class III/IV heart failure at the time of discharge* *In the setting of pre-existing heart failure or prior residence in an unfavorable location there must be at least a 1 class decrement (eg NYHA III -> IV)
 
Secondary Functional
 
 -Survival to hospital discharge, 30 and 90 days after initial OHCA -Favorable cerebral performance category (CPC) defined as 1 or 2 at discharge, 30 and 90 days after initial OHCA -Favorable modified Rankin score (mRS) defined as 0-3 at discharge, 30 and 90 days after initial OHCA -Favorable discharge destination or location of residence (30 and 90 days after OHCA) defined as home or acute inpatient rehabilitation -CPC-E at hospital discharge, 30 and 90 days after initial OHCA -Barthel Index of Independence in Activities of Daily Living (ADL) at discharge, 30 and 90 days after OHCA 
Neurologic
 
 -Estimated likelihood of good neurologic outcome (0-100%) assessed by an experienced (>3y) member of the PCAS team blinded to treatment assignment on day 0-3 post-ROSC. -Development of malignant EEG during hospitalization

	
 -Time (in hours) to awakening from ROSC; defined as following commands (all values > 96h assigned 100) -FOUR Motor + Brainstem scores on days 1-3 (requires 30 min off sedation; exclude endpoint if not medically permitted to pause sedation or paralysis) -Presence or absence of upper and lower extremity somatosensory evoked potential N20 on comatose patients obtained any time after post-arrest day 1. - Absolute value 24h after ROSC and change in value (24h vs 0h) of neuron specific enolase (NSE) -EEG burst suppression ratio and change in suppression ratio -EEG presence of dominant continuous background and reactivity to photic or tactile stimulation.

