2.5 STATISTICAL ANALYSIS

2.5.1 Sample Size Determination

Sample size calculations will be based on the primary composite endpoint and ascertained via a two sample test of proportions. The control rate proportion was estimated to be approximately 80-85% and we have > 80% power to detect reduction in the composite endpoint of approximately 23% with 60 per arm and a type II error rate of 5%, and 65 per arm assuming minimal dropout in the range of 5%. Since our estimates of dropout are extremely conservative (our reported dropout in EFIC studies is <1%)³² we are powered to detect changes in our primary composite endpoint as low as 21% if we actually observe little to no dropout. The secondary efficacy endpoint of iNO responsiveness is overpowered to detect a decrease in PA pressure in the region of 20-25 mm Hg with the planned enrollment.

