2.5.5 Handling Missing Data

Since our primary endpoint is ascertained at hospital discharge we expect no missing data though all analyses will be performed assuming a missing at random mechanism. No data imputation will be performed though standard sensitivity analyses, using standard missing data techniques may be used.

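### Defaulting unknown pre-arrest heart-failure class to NYHA I can score unchanged long-standing class III/IV as a primary event; the effect is small and toward no difference, and it is cheap to fix

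*Combined protocol and SAP*

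**What the plan says.** The primary endpoint (section 2.4 and the Protocol Synopsis) is a "Composite of in-hospital death, unfavorable discharge location, NYHA class III/IV heart failure at the time of discharge". A footnote limits it: "In the setting of pre-existing heart failure or prior residence in an unfavorable location there must be at least a 1 class decrement". Pre-arrest NYHA class therefore helps decide whether a given discharge class is an event.

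The baseline list in section 2.2 marks pre-arrest NYHA class as an essential element and gives a fallback: "if no surrogate is present and no medical records are found on the subject this will be assumed to be NYHA class I". The fallback needs both conditions, no surrogate and no records. The subject is not listed as a source.

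Section 2.5.5 expects no missing primary data and says: "No data imputation will be performed though standard sensitivity analyses, using standard missing data techniques may be used". It does not mention the NYHA default.

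Three other provisions bear on the point. Section 2.2 allows most baseline data to be collected retrospectively and schedules an NYHA assessment at discharge. Section 5.2 says that subjects who awaken will be told about the study.

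**The concern.** Take two survivors, both discharged home in class III and both in class III for years before the arrest. The one with a documented history has not worsened and is a non-event. The one without a surrogate or records is recorded as class I at baseline, appears to have fallen two classes, and is an event.

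Class I is the best possible value, so the default can only create events and never removes one. In-hospital deaths and unfavorable discharges are events whatever the baseline class, so the error is confined to survivors who would otherwise be event-free. An effective treatment enlarges that group in its own arm, so more of the false events would fall on iNO and the observed benefit would shrink. The subjects concerned have been discharged alive to home or acute rehabilitation, and many of them could probably be asked directly.

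**Working it through.** **Inputs from the documents.** Control event rate 80-85%; a reduction of about 23%, read as percentage points; 60 evaluable and 65 enrolled per arm (2.5.1); unadjusted two-sample test of proportions, two-tailed, p < 0.05 (2.5.2). Section 2.5.1 calls its 5% a type II error rate; I take it as the two-sided significance level, in line with 2.5.2.

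**Inputs not in the documents (assumptions).** u, the share of otherwise event-free survivors with neither surrogate nor records: 10-20%. h, the share of those who were truly in class III/IV before the arrest and leave unchanged: 5-15%. Then q = u × h runs from 0.10 × 0.05 = 0.5% to 0.20 × 0.15 = 3%.

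**The plan's own figure.** Power = Φ{[d − 1.96 √(2p̄(1−p̄)/n)] / √[(p₁(1−p₁) + p₂(1−p₂))/n]}, where p₁ and p₂ are the control and iNO event rates, d = p₁ − p₂ and p̄ is their mean. At n = 60 per arm:
- 80% vs 57%: 78.1%
- 82.5% vs 59.5%: 80.1%
- 85% vs 62%: 82.3%

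The stated power above 80% is reproduced to within 2 points over the control range.

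**Who can be misclassified.** Otherwise event-free survivors per 65:
- Control: 65 × 0.15 to 65 × 0.20 = 9.75 to 13
- iNO: 65 × 0.38 to 65 × 0.43 = 24.7 to 27.95
- Both arms: 34.45 to 40.95

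If iNO works as assumed, its share of false events is 0.43/(0.20 + 0.43) = 68% at an 80% control rate, or 0.38/(0.15 + 0.38) = 72% at 85%.

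**Expected false events.**
- Both arms: 34.45 × 0.005 = 0.17 to 40.95 × 0.03 = 1.23
- iNO: 24.7 × 0.005 = 0.12 to 27.95 × 0.03 = 0.84
- Control: 9.75 × 0.005 = 0.05 to 13 × 0.03 = 0.39

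**Effect on the comparison.** A true event rate p is observed as p + q(1 − p), so the observed difference is d(1 − q). A true 23 points becomes 23 × 0.995 = 22.9, or 23 × 0.97 = 22.3. At 60 per arm the power loss is about 0.3 points at q = 0.5%. At q = 3% it is 1.9 points (control 80%) or 1.6 points (control 85%). If the true rates are equal, the same q(1 − p) is added to both arms and the difference stays zero.

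**Stress case.** With u = 30% and h = 20%, q = 6%: 1.5-1.7 false events on iNO per 65, and a power loss of 3.4-3.8 points.

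**What one event can do** (two-sided pooled test, 65 per arm).
- Next to the boundary: 55/65 vs 45/65 gives p = 0.037; one more iNO event, 55/65 vs 46/65, gives p = 0.058.
- At about the design effect: 55/65 vs 40/65 gives p = 0.0030; 55/65 vs 41/65 gives p = 0.0052.

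**The case against.** The strongest reply is that the affected group may be nearly empty. The fallback requires no surrogate and no records, for someone who has survived a full admission and been discharged to home or acute rehabilitation. Section 2.2 expects no missing values for this element, and an admission history taken from the patient might itself count as a medical record. This largely stands as an argument about size. It does not remove the defect, because the protocol does not say whether index-admission notes count, and it foresaw the case clearly enough to write a rule for it.

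A reader might infer that the plan bars asking the survivor. It does not: asking is left out, not forbidden, and retrospective collection is allowed.

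A reader might take the remark in 2.3.3 that many patients come in "thus arriving without a family member from whom to obtain consent" as evidence that unknown histories will be common. That describes arrival, not discharge, and says nothing about records. It makes the situation plausible but gives no rate.

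The default could also be read as a breach of 2.5.5. That is debatable. It is a data-collection rule fixed in advance, like the fallbacks for arrest and ROSC times in the same list. What stands is that it acts as a single-value imputation inside the primary endpoint, and that 2.5.5 leaves sensitivity analyses optional and names none for it.

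Finally, the boundary example uses counts chosen next to the threshold, where any miscount would matter, and on the assumed ranges the expected number of false events on iNO is below one.

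**Conclusion.** The concern holds as a minor defect in how the primary endpoint is scored. A stated rule can turn unchanged class III/IV into an event, and the error runs one way. On assumed ranges of 10-20% unknown and 5-15% truly class III/IV, it amounts to about 0.2-1.2 subjects in the trial, under one on iNO, with a power loss below 2 points. The two shares are assumptions; the direction and the factor (1 − q) follow from the text, given that the same q applies in both arms.

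Two stronger readings are not supported. The first is that the default threatens the validity of a positive result. The arm imbalance exists only if the arms differ in event-free survivors; with no difference the false events are balanced and type I error is not inflated. The second is that the parallel defaults for pre-arrest CPC and mRS do the same harm. Section 2.4 defines favorable CPC and mRS by absolute cut-offs with no baseline adjustment, so those defaults change no listed endpoint.

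**What to change.** In section 2.2, state that when pre-arrest NYHA class is unknown it will be obtained, before the composite is scored, from the survivor, a surrogate found later or the index-admission history. Flag any value that still defaults to class I. In 2.5.5, commit to reporting the primary result with the NYHA component of the flagged subjects scored both ways: as an event and as a non-event.

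The cost is a sentence or two of text, one question at a discharge assessment that already takes place, and one extra line in the results. No patients or procedures are added. The small downside is that baseline class would be recalled after the outcome, by people who have been comatose. They remain blinded to treatment, so recall error should not differ by arm because of knowledge of assignment.
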